- Proportion of compliant platelet transfusion actions (examples of noncompliance are transfusion given at or above threshold or without any platelet count in the previous 12 hours, excluding transfusions given during a temporary suspension, or transfusion not given within 12 hours of a platelet count below threshold) > 90% (see Appendix F for details);
- Proportion of patients with one or more temporary suspensions not due to preparation for decannulation < 10%;

- 8. Proportion of patients who withdraw from the study and/or are lost to follow-up (i.e., withdraw and/or are missing 90-day mortality assessment) < 6%;
- Proportion of patients with non-platelet transfusion protocol violations (violation of sitespecific management protocol for any aspect besides platelet transfusion threshold compliance) < 5%;
- 10. First instance of progression to severe bleeding or thrombotic outcomes can be adjudicated in > 90% of the patients for whom such an outcome was reported by the site.

Similar to pre-transfusion platelet counts, overall platelet transfusion doses, and progression to severe bleeding and/or clotting, feasibility outcomes 1, 6, and 9, are to be analyzed outside of temporary suspensions.

C. Tertiary Outcomes

Our tertiary outcome is to demonstrate the ability for an adjudication committee to determine the severity of bleeding and/or thrombotic outcomes.

This is similar to the primary safety outcome, except that it does not include mortality in the definition. That is, progression to severe bleeding or a severe clotting event must occur, whether or not there is an all-cause death. We will demonstrate that the recorded data is sufficient for the adjudication of severe bleeding, severe thrombus or both in 90% of enrolled subjects with this outcome reported by the site.

Justification of BASIC and NHLBI definitions of bleeding and thrombosis:

We believe that the BASIC (34) (Table 1) and NHLBI definitions (48) of bleeding and thrombosis provide the most relevant descriptions as they relate to children supported by ECMO. Importantly, central nervous system involvement, a frequent site of bleeding on ECMO, may be captured by a

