The sixth feasibility criterion's outcome is defined for a combination of platelet-count level and platelet-transfusion-level observations. Adherence is indicated by having an appropriately dosed platelet transfusion within 12 hours after a below-threshold platelet count, and by not having any platelet transfusion when there is no below-threshold platelet count. In general, there is one adherence/non-adherence determination per platelet count (although some are excluded, and some additional determinations can apply when a transfusion occurs without any platelet count in the previous 12 hours).

	,	Platelet Transfusion			
		Yes	Νο	Excluded transfusion(s) was the only transfusion within 12 hours after platelet count ^a	
Platelet count	Yes	Adherence ^{b,c}	Non-adherence ^c	Adherence	
below threshold	No	Non-adherence ^b	Adherence	ignored	
	Excluded platelet count ^d	Non-adherence ^b	ignored	Ignored	

^a Platelet transfusions are excluded if any of the following apply: transfusion start time before randomization or after the time the strategy was permanently terminated; transfusion start time during a period of temporary suspension

^b The transfusion is considered non-adherent if an included (i.e., not excluded) platelet transfusion did not have a below-threshold platelet count as the most recent platelet count, or if there was an absence of a platelet count within 12 hours prior to the transfusion start time, or the most-recent platelet count was at or above the threshold.

^c The platelet count is considered non-adherent if an included (i.e., not excluded) platelet count was below the threshold and there was no platelet transfusion (not known to be at an inappropriate dose) within 12 hours after the platelet count.

^d Platelet counts are excluded if any of the following apply: was more than 12 hours prerandomization; was after the time the strategy was permanently terminated; was prior to randomization, and before randomization had a transfusion and/or another pre-randomization platelet count; was a below-threshold count but within 12 hours after the blood sample was collected, and prior to a subsequent platelet transfusion, there was either a platelet count at or above the threshold or the transfusion strategy was permanently terminated; was a platelet count at or above the threshold but within 12 hours and prior to a blood transfusion, there was either a below-threshold platelet count or the transfusion strategy was permanently terminated.

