Calculation: Adherence % = 100% * (Adherences)/(Adherences + Non-adherences)

Feasibility Criterion 6 Threshold: Adherence > 90%

Statistical Analysis Plan

Protocol Title: ECMO Hemostatic Transfusions in Children

Protocol Version and Date: 1.3.1; July 14, 2023 (BRANY IRB approved July 19, 2023)

SAP Authors: [name] (with reuse of protocol and DCC template language)

SAP Version and Date: 1.0; November 9, 2023

CONFIDENTIAL

Approvals:

Approved By:		
DocuSigned by:	Sutdy PI	
[name]		11/10/2023
N 25066330F4F748A	Title	Date
DocuSigned by:	Study PI	
[name]		11/10/2023
Na891D9374C814C7	Title	Date
DocuSigned by:	Co-I,	
[name]	Statistician	11/10/2023
Nacie D23B98F4BB	Title	Date

Contents

	Abbreviations	v
1	1.1 Purpose of SAP	1 1 1
2	 2.1 Study Objectives	$1 \\ 1 \\ 1 \\ 2 \\ 2 \\ 6 \\ 7 \\ 8$
3	3.1 Overall Study Design	0 0
4	STUDY SUBJECTS AND ANALYSIS POPULATIONS14.1 Eligibility14.2 Populations for Analyses14.2.1 Screening Population14.2.2 Inclusion Population14.2.3 Eligible Population14.2.4 Approached Population14.2.5 Consented Population14.2.6 Intention-to-Treat Population14.2.7 Safety Population1	1 1 1 1 2 2 2
5	GENERAL ISSUES FOR STATISTICAL ANALYSES135.1 Analysis Software135.2 Methods for Withdrawals, Missing Data, and Outliers135.3 Multiple Comparisons and Multiplicity13	$\frac{3}{3}$

	$5.4 \\ 5.5 \\ 5.6$	Planned Subgroups, Interactions, and Covariates	14 14 14
6	INT 6.1 6.2 6.3 6.4 6.5 6.6	CERIM ANALYSES Frequency of and Timepoints for Interim Analysis Stopping Rules for Interim Efficacy Analysis Futility Monitoring in the Interim Analysis Early Trial Termination for Safety Subgroups in the Interim Analysis Blinding in the Interim Analysis	 15 15 15 15 17 17
7	PL 7.1 7.2 7.3 7.4 7.5 7.6 7.7	ANNED ANALYSESDescription of Participant CharacteristicsPrimary Outcome Analysis7.2.1Primary Analysis for Aim 17.2.2Additional AnalysesSecondary Outcomes Analyses (Analyses for Aim 2)7.3.1Primary Analysis for Aim 2Tertiary Outcome AnalysisAdditional Outcome AnalysesTechnical Approaches for Subgroup AnalysesSafety Analyses	 17 17 18 19 19 19 20 20
8	SAI	MPLE SIZE DETERMINATION	21
9	Ref	erences	22
		pendix: INTERIM STOPPING RULE OPERATING CHARACTER- ICS	23
A	Inte	erim stopping rule considerations	23
в			24

Abbreviations

Abbreviation	Definition
AIC	Akaike Information Criterion
APPROACHED	Approached Population; see Section 4.2
BP	Blood Pressure
$\operatorname{CAR}(1)$	Continuous analog of first-order AutoRegressive process

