- Endpoint: 100% × (# of compliant transfusions not during a temporary suspension)/ (# of transfusions not during a temporary suspension + number of transfusions that should have been given but were not)
- Feasibility threshold: >90%

(SE7) Transfusion strategy suspension (not due to preparation for decannulation) percentage

- Outcome: For each patient in the ITT population (see Section 4.2.6), whether the patient had at least one temporary suspension of the transfusion threshold not due to preparation for decannulation before the permanent discontinuation of the treatment strategy. A temporary suspension of the transfusion threshold will not require a transfusion in excess of the threshold to have been given during the suspension period for it to be counted as a suspension
- Endpoint: $100\% \times (\# \text{ in ITT population with at least one temporary suspension of the transfusion threshold not due to preparation for decannulation) / (# in ITT population)$
- Feasibility threshold: < 10%

(SE8) Withdrawal and/or lost-to-follow-up percentage

- Outcome: For each patient in the ITT population, whether the patient was withdrawn from study participation by 90 days post-randomization and/or had an unknown mortality status for the timepoint of 90 days after randomization. The 90-day vital status will be considered known if the 90-day communication for mortality assessment is completed within ± 10 days, inclusive, of 90 days after randomization, or if the patient was known to have already died (e.g., died while on ECMO) such that the 90-day follow-up mortality assessment is unnecessary
- Endpoint: $100\% \times (\# \text{ in ITT population who were withdrawn from the study by 90 days after randomization or had unknown 90-day mortality) / (# in ITT population)$
- Feasibility threshold: < 6%

(SE9) Percentage with any violations of local non-study-specific circulatory support protocols

• Outcome: For each patient in the ITT population, whether the patient had any reported instances of non-adherence to the site's non-study-specific circulatory support strategies. For this outcome, any instances of platelet transfusions above the randomized threshold are immaterial; on the other hand, for example, if the anticoagulation

strategy in place at the site was not followed, this is considered a protocol violation for this outcome. The site PIs will determine whether or not local protocols were followed

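### SAP SE6 and protocol Appendix F compute the same >90% compliance criterion by different formulas; the SAP should be conformed to Appendix F

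*Combined protocol and SAP*

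**What the plan says.** **SAP v1.0, section 2.2.2 (SE6).** The outcome sits at the level of the transfusion. The numerator is compliant transfusions outside temporary suspensions. The denominator is all transfusions outside suspensions plus the "number of transfusions that should have been given but were not". A platelet count at or above threshold that is followed by no transfusion enters neither term. The cut is >90%. The SAP title page gives "Protocol Version and Date: 1.3.1; July 14, 2023" as the protocol it was written to.

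**Protocol v1.4 (April 22, 2024).** Section 8.D describes criterion 6 as a combined measure of counts and transfusions and refers to Appendix F. Criterion 6 in section 9.B carries the same cut and the same pointer: "> 90% (see Appendix F for details". Appendix F states: "In general, there is one adherence/non-adherence determination per platelet count". It credits two kinds of conduct. The first is treatment of a low count: "Adherence is indicated by having an appropriately dosed platelet transfusion within 12 hours after a below-threshold platelet count". The second is restraint: adherence is also shown "by not having any platelet transfusion when there is no below-threshold platelet count". The percentage is adherences over adherences plus non-adherences.

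**The concern.** Both formulas serve one yes/no criterion with one cut. SAP 7.3.1 decides SE2 to SE10 by comparing the estimate with its threshold, so the choice of formula can decide the verdict. A statistician who programs from the SAP would compute something other than what the current protocol defines. The independent programming in SAP 5.6 would not expose this if both programmers work from the SAP.

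Appendix F adds correct non-transfusions to numerator and denominator alike, so its percentage will typically be the higher of the two. If the mismatch is noticed only after the data are in, choosing between a failing and a passing figure would look like choosing the answer. The compliance figure also feeds the design of the full trial.

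**Working it through.** The documents report no SE6 value to reproduce, so the check compares the two formulas.

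**1. A count example (assumed figures).** Take 100 included counts, 30 below threshold. Of these 30, 27 are transfused and 3 missed. Of the 70 at or above threshold, 3 are transfused and 67 are not.

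- SAP: 27 / (27 + 3 + 3) = 27/33 = 81.8%, fail.
- Appendix F: (27 + 67) / 100 = 94.0%, pass.

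**2. General form.** Let b be the share of included counts that are below threshold, m the misses per below-threshold count, and o the off-threshold transfusions per below-threshold count, each following a count at or above threshold.

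- SAP = (1 − m) / (1 + o)
- Appendix F = 1 − (m + o)b

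**3. A range for b.** Protocol 6.A expects 66% of patients to be transfused on any given ECMO day. Protocol 8.A requires at least two counts a day and a further count after each transfusion. I assume one transfusion per transfusion day and one below-threshold count per transfusion. I also assume that footnote d of Appendix F removes one at-or-above count per below-threshold count.

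- Post-transfusion count additional to the two scheduled ones: 2 + 0.66 − 0.66 = 2.00 included counts a day, so b = 0.66/2.00 = 0.33.
- Post-transfusion count doubling as a scheduled one: 2 − 0.66 = 1.34, so b = 0.66/1.34 = 0.4925.

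More than one transfusion a day raises b, so 0.7 is shown as well.

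**4. Equal error rates, m = o = e.** The SAP formula fails once e reaches 0.1/1.9 = 5.3%. Appendix F fails once e reaches 0.05/b. SAP compliance of 85% means e = 0.15/1.85 = 8.11%.

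| b | Appendix F when the SAP ratio is 85% | Range of e in which the verdicts differ |
|---|---|---|
| 0.33 | 1 − 2(0.0811)(0.33) = 94.6%, pass | 5.3% to 15.2% |
| 0.4925 | 92.0%, pass | 5.3% to 10.2% |
| 0.7 | 88.6%, fail | 5.3% to 7.1% |

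The gap closes at b = 0.95, where 0.05/0.95 = 5.3%.

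**5. One kind of error only.** With m = 15% and o = 0, the SAP gives 85.0%. With m = 0 and o = 15%, it gives 1/1.15 = 87.0%. Appendix F is 1 − 0.15b in both cases: about 95% at b = 0.33, 92.6% at 0.4925 and 89.5% at 0.7. The conflict does not depend on equal error rates.

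**6. Other scoring differences in the text.**

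- *Superseded counts.* Appendix F excludes a low count that is superseded within 12 hours by one at or above threshold before any transfusion, in line with protocol 8.A. The SAP treats any below-threshold count as an indication, so read literally it scores such a count as missed.
- *Suspensions.* Appendix F credits a low count whose only transfusion fell within a suspension. The SAP ignores that transfusion.
- *Dose.* The SAP needs the site principal investigators to agree that the dose was the proper one. Appendix F footnote c accepts a transfusion "not known to be at an inappropriate dose". The two part only when the propriety of the dose is undetermined.

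**The case against.** The strongest reply is that this is document lag with a clear resolution. A reader might infer that the plan leaves open which definition governs. The documents do not support that: protocol 8.D and 9.B both name Appendix F for criterion 6, and the SAP ties itself to an older protocol version. This stands, and the fix below relies on it. There is, however, no express precedence clause, and SAP 1.2 presents the SAP as the outline of the planned analyses, so a programmer could reasonably follow it.

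A reader might also infer that the SAP was never brought into line. Only SAP v1.0 is supplied, and a later one cannot be excluded.

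Nor is the SAP vague about what a miss is. Section 2.2.2 equates an indication with a below-threshold count, and section 3.4 defines a miss per such count.

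The illustration also has limits. It holds b fixed as misses rise, although an untreated patient may produce further low counts, each of which Appendix F can score as non-adherent. That pulls the Appendix F figure down. It could even fall below the SAP ratio if SAP misses were tallied per transfusion due, although section 3.4 points to a tally per count. Appendix F is therefore typically, not always, the more lenient.

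Finally, protocol 8.D cites adherence of 97% and 92% in similar trials. If those were SAP-type ratios, both formulas would pass: at 92%, e = 0.08/1.92 = 4.2% and Appendix F is 97.2% to 95.9% for b from 0.33 to 0.4925. The protocol does not say how either figure was measured, so this gives limited reassurance.

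**Conclusion.** The conflict is real: two formulas that can disagree stand behind one >90% criterion, and the supplied SAP does not match the current protocol. For b between 0.33 and 0.49 and equal error rates, the verdicts differ once errors reach 5.3%, up to about 15% or 10% respectively. At a SAP ratio of 85%, Appendix F passes across that range but fails at b = 0.7. The error rates are assumed, because the documents give none, and b rests on the simplifications listed in the working.

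It would be too strong to say that the go decision hinges on this. SE6 changes the 5-of-10 result only if exactly four of the other nine criteria are met and compliance falls in the band where the formulas disagree. The amendment should still be made before analysis, because the verdict on a named criterion should not depend on which document the programmer opens.

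**What to change.** Before analysis, amend SAP 2.2.2 (SE6) to the Appendix F definition, including its count and transfusion exclusions and its scoring rules for suspensions and dose. In SAP 3.4, change only the cross-reference to SE6. Keep that section's patient-level all-or-none measure, which captures missed transfusions, and its split of transfusions by suspension status.

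Report the transfusion-based ratio descriptively beside the governing figure, because correct non-transfusions can dilute transfusion errors.

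The cost is one SAP amendment and one programming update, with no new data. The downside is two compliance figures to explain, of which the governing one can look the more favourable.

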2.2.3 Tertiary Outcome(s)

The tertiary outcome is whether the adjudication committee was able to reach an adjudication decision for progression to severe bleeding and/or a severe thrombotic event. Note that the outcome of progression to severe bleeding and/or severe thrombosis is similar to the primary safety outcome, but the primary safety outcome also includes mortality while the tertiary outcome disregards mortality as a sufficient condition (though it is anticipated that mortality may have already involved a severe bleeding and/or thrombotic event, making the distinction less impactful). This patient-level outcome will be defined for those who have a site-reported progression to severe bleeding and/or severe thrombosis and will use each such patient's first reported instance of a progression to severe bleeding or severe thrombosis. Note that this tertiary outcome is the same as defined in SE10.

2.2.4 Additional Outcome(s)

Additional outcomes mentioned in the protocol include the following, which include most of the measures recommended in [1].

- Hemorrhagic complications according to the ELSO definition
- Thrombotic complications according to the ELSO definition
- Blood product exposure, defined as the total number of transfusions (red blood cell, plasma, platelets, cryoprecipitate, fibrinogen concentrate) and other hemostatic therapies (activated Factor VII, tranexamic acid, aminocaproic acid, DDAVP, and von Willebrand factor, etc.)
- Re-explorations and other surgical procedures to treat bleeding
- Duration of ECMO, defined as 90-day ECMO-free days (e.g., if a patient is decannulated after 7 days, the 90-day ECMO-free days is 83 days; whereas if a patient dies on ECMO after 7 days, the 90-day ECMO-free days is 0 days)
 - This is defined based on calendar days for days 1–90, with day 1 being the day of randomization and day 90 being 89 calendar days after randomization, and because every randomized patient will be on ECMO on day 1, the range for this outcome is 0–89
- Length of Pediatric Intensive Care Unit (PICU) stay, defined as the 90-day PICU-free days (as with ECMO-free days, using calendar days and with possible range of 0–89)
- Discharge Pediatric Overall Performance Category (POPC)
- Discharge Pediatric Cerebral Performance Category (PCPC)
- Mortality on ECMO
- Mortality within 24 hours of the treatment strategy being permanently discontinued
- Mortality at 28 days (obtained on or after 28 days after randomization, unless known death before)
- Mortality at 90 days (obtained on or after 80 days after randomization, unless known death before)
- Number of temporary suspensions of the transfusion strategy

2.2.5 Safety Outcome(s)

Many safety outcomes are obtained during the *acute follow-up period*, defined as the period beginning with randomization and ending 24 hours after the permanent discontinuation of the transfusion strategy. The transfusion strategy for a randomized patient is permanently discontinued at the earliest of any of the following five events: (1) per site report, progression to severe bleeding, according to the BASIC definition, and/or severe clotting, and/or death; (2) decannulation from ECMO; (3) twenty-one days post-randomization (as the progression to new bleeding and new thrombosis has plateaued by day 21 and $\approx 95\%$ of the patients will be off ECMO by then); 4) temporary suspension lasting more than 24 hours; or 5) study withdrawal.

The primary safety outcome is defined at the patient level for all patients in the ITT population. It is defined as the occurrence of any of the following during the acute follow-up period: progression to severe bleeding (defined below); progression to severe thrombosis (defined below); death. The outcome is initially site-reported but then is to be adjudicated by the adjudication panel. If the panel determines the outcome criteria were not met, the outcome will be considered not to have occurred. Otherwise, if the panel confirms the criteria were met, or if the panel is unable to reach a determination, the primary safety outcome will be considered to have occurred.

Using the BASIC definition [2], severe bleeding will be defined as:

- 1. Bleeding that leads to at least one organ dysfunction, using PELOD-2 score criteria of organ dysfunction
- 2. Bleeding that leads to hemodynamic instability, defined as an increase in heart rate (HR) by > 20% from baseline or a decrease in blood pressure (BP) by > 20% from baseline (i.e., prior to the bleeding event)
- 3. Bleeding leading to a drop in hemoglobin >20% within 24hr
- 4. Quantifiable bleeding $\geq 5 \text{ mL/kg/hr}$ for $\geq 1 \text{hr}$ (e.g., chest tube)
- 5. Intracranial hemorrhage on computerized tomography (CT) scan or head ultrasound
- 6. Intraspinal bleeding leading to loss of neurologic function below the lesion, nontraumatic intra-articular bleeding leading to decreased range of movement, or intraocular bleeding leading to impaired vision.

Severe thrombotic events will be defined according to the NHLBI Hemostasis Clinical Trial Outcomes Working Group as any of the following, as diagnosed clinically: circuit clot requiring circuit change; need for thrombectomy; ischemic stroke; or distal thromboembolism. [3]

Other patient-level safety outcomes include:

- the occurrence of any adverse event (AE) that is non-serious but at least possibly related to the platelet transfusion strategy
- the occurrence of any serious adverse event (SAE)
- the occurrence of any SAE, or of any non-serious AE at least possibly related to the platelet transfusion strategy (i.e., either of the two outcomes mentioned immediately above)
- the occurrence of any serious adverse event at least possibly related to the platelet transfusion strategy.

As with the primary safety outcome, the period during which new adverse events are to be identified for subsequent entry in the study database is the acute follow-up phase from randomization through 24 hours after the transfusion strategy was permanently discontinued. Note that adverse events are recorded if they are non-serious but deemed at least possibly related to the study intervention (transfusion strategy), or if they are serious regardless of study-relatedness.

